### 6.3.7 Immunologic Studies

#### CD4+/CD8+ for Groups A, B, & C

Obtain absolute CD4+/CD8+ count and percentages at entry from a laboratory that possesses a CLIA certification or equivalent (**US sites**) or **IQA certification (non-US sites)**.

Note: If a CD4+/CD8+ count has been drawn for clinical care within the last 45 days, it may be used. This laboratory does not have to provide documentation of GCLP or EQA.

### 6.3.8 Virologic Studies

#### Plasma HIV-1 RNA for Groups A, B, & C

At entry, HIV-1 RNA must be performed by a laboratory that possesses a CLIA certification or equivalent (**US sites**) or **VQA certification (non-US sites)**.

Note: If plasma HIV-1 RNA has been drawn for clinical care within the last 45 days, it may be used. This laboratory does not have to provide documentation of GCLP or EQA.

### 6.3.9 Pharmacokinetic Sampling

Plasma will be obtained for LNG concentrations. Participants will have blood sampling within 30 minutes prior to LNG EC administration, and then 0.5, 1, 1.5, 2, 3, 4, 6, 8, 24, and 48 hours after administration of LNG EC. Participants may leave the clinical site after the 8 hour sample, and return for the 24- and 48-hour samples.

From the same samples collected for LNG analysis, measurement of EFV (Groups A and B), DTG (Group C), and RIF (Group D) concentrations will occur. EFV will be assessed from a sample collected 12-20 hours after the last dose of EFV. DTG or RIF will be assessed from a plasma sample collected 20-28 hours after the last dose of DTG or RIF. To accommodate this timing, EFV should be administered in the evening prior to the entry PK visit and if RIF or DTG are given in the morning, collect pre-dose LNG sample prior to administered DTG or RIF. See the MOPS for further instructions on timing.

The three doses of EFV, DTG, or RIF prior to the entry PK sampling period should be documented on the eCRF. Any EFV, DTG, or RIF dose administered

during the Day 0 PK visit should be documented. On Day 1 and Day 2, document any EFV, DTG, or RIF dose administered since the previous visit.

Additional details regarding LNG, ART, or RIF PK, please see [section 11.3](#), the MOPS, and the laboratory processing chart (LPC) found on the A5375 PSWP.

#### 6.3.10 Whole Blood for Pharmacogenetic Assessment

A single whole blood sample will be obtained from all study participants for human genotyping of polymorphisms that have been associated with metabolism and/or transport of the study drugs, including EFV (e.g., CYP2B6), RIF (e.g., SLCO1B1), and LNG. See the LPC on the A5375 PSWP for details regarding processing and shipping.

If the whole blood for drug metabolism genotype is not obtained at entry, this sample may be obtained at any later visit.

#### 6.3.11 Hair Sampling

Hair samples will be collected per the SOE from participants to measure concentrations of EFV (Groups A and B), DTG (Group C), and INH (as a surrogate of adherence to RIF in Group D), to evaluate adherence to ART or anti-TB therapy at the time of LNG EC administration. Participants may opt-out of the hair collection procedure and remain enrolled in the study.

Please see [section 11.3](#), the MOPS, and the LPC found on the A5375 PSWP for more details regarding hair sampling.

#### 6.3.12 Adherence Assessment (ART and TB drugs)

Adherence to ART or TB drugs will be assessed per the SOE using the ACTG self-report questionnaires completed by the participant or completed with the help of site staff (counselor- or nurse-driven). Adherence to the relevant ART or TB drug at study entry will be further verified by collecting a plasma and hair specimen on that day for measuring ARV or INH/RIF concentrations. For sites with clinics located at a different location from the TB and ARV clinic, study staff will be encouraged to work closely with TB and ARV providers for monitoring of adherence to medication.

The adherence eCRF is posted on the DMC Portal in the Forms Management Utility.

#### 6.3.13 Acceptability and Practicality Questionnaire

The acceptability and practicality questionnaire will collect information about the participant's experience of side effects known to be associated with LNG EC single dose, per the SOE. At entry, participants will also be asked about

relationship status, level of education, prior experience with EC, sex that could lead to pregnancy, and pregnancy intention.

At entry, the acceptability and practicality questionnaire will be collected via participant interview and entered on the questionnaire. **An entry, the Current Symptoms portion of this questionnaire should be collected prior to LNG dose receipt.**

**NOTE: The discomfort/bothersome scale in the Current Symptoms questionnaire is NOT equivalent to the DAIDS grading table for reportable adverse events (please refer to protocol section 7.2), which has particular and more rigorous criteria the event must fulfill to be reported.**

Post-entry, the acceptability and practicality questionnaire may be collected by remote contact interview or during a site visit.

Questionnaires are posted on the DMC Portal in the Forms Management Utility.

#### 6.3.14 Site Acceptability and Practicality Questionnaire

Each participating site will complete a Site Acceptability and Practicality Questionnaire per the Schedule of Site Evaluations ([Table 6.1-2](#)).

## 7.0 ADVERSE EVENTS AND STUDY MONITORING

### 7.1 Definition of Adverse Events

An adverse event (AE) is any unfavorable and unintended sign (including an abnormal laboratory finding), symptom, or diagnosis that occurs in a study participant during the conduct of the study REGARDLESS of the attribution (i.e., relationship of event to medical treatment/study product/device or procedure/intervention). This includes any occurrence that is new in onset or aggravated in severity or frequency from the baseline condition.

### 7.2 Adverse Event Collection Requirements for this Protocol

AEs must be recorded on the eCRFs if any of the following criteria have been met:

- All Grade  $\geq 3$  AEs considered potentially or definitely related to LNG
- All Grade  $\geq 2$  nausea
- All Grade  $\geq 2$  diarrhea
- All Grade  $\geq 2$  menorrhagia or metrorrhagia
- Ectopic pregnancy (see EAE reporting requirements [section 7.3.2](#))
- All AEs meeting Serious Adverse Event (SAE) definition or Expedited Adverse Event (EAE) reporting requirement

Note **A**: Normal menses are not a reportable event.

**Note B:** Events meeting EAE reporting requirements should also be entered into the DAIDS Adverse Experience Reporting System (DAERS), an Internet-based reporting system.

All AEs that are reported must have their severity graded. To grade AEs, sites must refer to the DAIDS AE Grading Table, corrected Version 2.1, July 2017.

In addition, Addendum 1, Female Genital Grading Table for Use in Microbicide Studies, Version 1.0 – November 2007, will be used for vaginal symptoms and abnormal uterine bleeding unrelated to pregnancy.

Both grading tables are available on the DAIDS RSC website at <https://rsc.niaid.nih.gov/clinical-research-sites/daids-adverse-event-grading-tables>.

#### Serious Adverse Events (SAEs)

An SAE is defined as any untoward medical occurrence that:

- Results in death
- Is life-threatening
- Requires inpatient hospitalization or prolongation of existing hospitalization
- Results in persistent or significant disability/incapacity
- Is a congenital anomaly/birth defect
- Is an important medical event that may not be immediately life-threatening or result in death or hospitalization but may jeopardize the patient or may require intervention to prevent one of the other outcomes listed in the definition above.

### 7.3 Expedited Adverse Event (EAE) Reporting to DAIDS

#### 7.3.1 Expedited Reporting of Adverse Events to DAIDS

Requirements, definitions and methods for expedited reporting of Adverse Events (AEs) are outlined in Version 2.0 of the DAIDS EAE Manual, which is available on the RSC website at <https://rsc.niaid.nih.gov/clinical-research-sites/manual-expedited-reporting-adverse-events-daids>.

The DAIDS Adverse Experience Reporting System (DAERS), an internet-based reporting system, must be used for EAE reporting to DAIDS. In the event of system outages or technical difficulties, EAEs may be submitted using the DAIDS EAE Form. This form is available on the DAIDS RSC website at <https://rsc.niaid.nih.gov/clinical-research-sites/paper-eae-reporting>.

For questions about DAERS, please contact NIAID CRMS Support at [[contact]](mailto:[contact]). Please note that site queries may also be sent from within the DAERS application itself.

For questions about expedited reporting, please contact the DAIDS RSC Safety

Office at [[contact]](mailto:[contact]).

### 7.3.2 Reporting Requirements for this Study

- The suspected, unexpected serious adverse reaction (SUSAR) Reporting Category, as defined in Version 2.0 of the DAIDS EAE Manual, will be used for this study.
- The study agent for which expedited reporting is required is: levonorgestrel emergency contraception (LNG EC).
- In addition to the EAE Reporting Category identified above, other AEs that must be reported in an expedited manner are:
  - Ectopic pregnancies.

### 7.3.3 Grading Severity of Events

The DAIDS AE Grading Table corrected Version 2.1, July 2017, must be used.

In addition, Addendum 1, Female Genital Grading Table for Use in Microbicide Studies, Version 1.0 – November 2007, will be used for vaginal symptoms and abnormal uterine bleeding unrelated to pregnancy.

Note: normal menses are not a reportable event.

Both grading tables are available on the DAIDS RSC website at <https://rsc.niaid.nih.gov/clinical-research-sites/daids-adverse-event-grading-tables>.

### 7.3.4 Expedited AE Reporting Period

- The expedited AE reporting period for this study is as per the DAIDS EAE manual.
- After the protocol-defined EAE reporting period, unless otherwise noted, only SUSARs, as defined in Version 2.0 of the DAIDS EAE Manual, will be reported to DAIDS if the study staff become aware of the events on a passive basis (from publicly available information).

## 7.4 Study Monitoring

The protocol core team will monitor the conduct and safety of the study via regular summaries of accrual, study discontinuation, data completeness, and AEs, as appropriate.

The DAIDS **Clinical Representatives** will review and assess select EAE reports for potential impact on study participant safety and protocol conduct as per DAIDS policies, guidance documents, and SOPs, as applicable. Additionally, the DAIDS Clinical Representative will review aggregated adverse event summaries by open-label group **as distributed in the core team monitoring report described above, which will be distributed at least** every 6 months by SDAC.

The study will undergo interim review at least annually by an ACTG-appointed Study Monitoring Committee (SMC). The first interim review will occur no more than 1 year after the enrollment of the first study participant or 3 months after 25 women have completed the study, whichever occurs earlier. An interim review may also be convened if a concern is identified by the DAIDS Clinical Representative, the study chairs, or study statistician in consultation with the team. See [section 10.0](#) for statistical and other considerations related to interim monitoring.

Detailed plans for study monitoring will be outlined in a Study Monitoring Plan developed by the Statistical and Data Management Center (SDMC) prior to enrollment of the first participant.

## 8.0 CLINICAL MANAGEMENT

### 8.1 Toxicity

Toxicities will be evaluated and managed by the site staff in close consultation with the participants' primary care clinicians. Ongoing communication between the ACTG site staff and the participants' clinicians is encouraged. If a toxicity is identified, the ACTG site staff is encouraged to communicate with primary care providers as soon as possible.

If TB medication or ART is held for toxicity by the primary care physician, participants must inform the site staff. Information about these treatment modifications/interruptions must be recorded on the source document and eCRF.

Grades 1 and 2: Can be managed as per standard of care by the study doctor or local physician.

Grades 3 and 4: Participants must be stabilized and referred immediately to obtain treatment at local hospital, if required.

Vaginal Bleeding: Grade  $\geq 2$  must be closely monitored and managed as per standard of care.

Diarrhea: Grade 2 should be managed per standard of care by the study doctor or local physician. Participants with Grades 3 and 4 diarrhea must be stabilized and referred.

### 8.2 Pregnancy

Pregnancy and pregnancy outcome will be recorded on the eCRFs. Pregnancies that occur on study should be reported prospectively to The Antiretroviral Pregnancy Registry. More information is available at [www.apregistry.com](http://www.apregistry.com). [contact]; [contact]. (For studies conducted at sites outside the United States, report to The Antiretroviral Pregnancy Registry—[contact]; [contact] or [contact].)

### Pregnancy Outcomes and Reporting

If a woman has completed the study or chooses to discontinue from the study before the end of the pregnancy, then site staff should request permission to contact her regarding pregnancy outcomes at the end of pregnancy. If the information is obtained, pregnancy outcomes will be submitted on an eCRF at the end of the pregnancy.

### 8.3 Breastfeeding

Breastfeeding is discouraged at sites where alternative feeding options are feasible and available. Sites should follow local guidelines to prevent mother-to-child transmission during breastfeeding.

## 9.0 CRITERIA FOR DISCONTINUATION

### 9.1 Premature Treatment Discontinuation

Because the study treatment is a single dose, this section does not apply. See section 9.2 for Study Discontinuation.

### 9.2 Premature Study Discontinuation

- Participant fails to complete PK specimen draws over the 8-hour period following study treatment
- Participant fails to initiate/take study treatment within 7 days of enrollment
- Participant has a positive pregnancy test prior to LNG EC administration
- Request by the participant to withdraw
- Request of the primary care provider if she or he thinks the study is no longer in the best interest of the participant
- At the discretion of the IRB/EC, FDA, NIAID, Office for Human Research Protections (OHRP), other government agencies as part of their duties, or investigator

Note: If the participant discontinues before evaluations for the primary outcome have been completed, the participant will be replaced.

## 10.0 STATISTICAL CONSIDERATIONS

### 10.1 General Design Issues

A5375 is a Phase II, prospective, partially randomized, open-label, multi-center controlled clinical trial designed to investigate the appropriate dosing of “single dose” levonorgestrel (LNG – intended to be used as EC), among women who are taking medications that might have PK interactions with LNG, such as particular anti-HIV ART regimens or an anti-TB regimen. This parallel group, DDI PK study has two directly assigned groups, and two randomized groups for a total of four distinct study groups:

women on DTG-containing ART regimens and women on RIF-containing TB regimens will be directly assigned to Groups C and D, respectively; and women on EFV-containing ART regimens will be randomized in a 1:2 ratio to Groups A and B, respectively.

Study treatment is LNG EC given once following entry evaluation completion in a directly observed manner: Groups A and C will receive standard dose of LNG 1.5 mg, and Groups B and D will receive double dose of LNG 3.0 mg. Absence of blinding does not affect study integrity via bias due to a number of study design factors including the following: directly observed administration of a study treatment that consists of only a single dose (i.e., one time versus longitudinal intervention), and the primary study outcome is an objectively assessed PK parameter (AUC). The key study evaluation is an intensive, 8-hour PK sampling around this one dose of study treatment. Length of study follow-up is 4 weeks for each participant, but follow-up subsequent to the 48-hour PK assessment will be performed remotely.

Women on the qualifying targeted concomitant medication regimens must not be pregnant, within 6 weeks postpartum, breastfeeding an infant under 6 months of age, or currently using other hormonally based contraception.

The primary completion date for each woman is one day after study treatment administration.

## 10.2 Outcome Measures

### 10.2.1 Primary Outcome Measure

10.2.1.1 Area under the Curve over 8 hours (AUC0-8h) for LNG.

### 10.2.3 Exploratory Outcome Measures

10.2.3.1 Concentration of targeted concomitant medication (e.g., DTG, EFV, and INH) in hair sample collected at entry as measure of long-term concomitant medication adherence.

- 10.2.3.2 Specific plasma concentration of targeted concomitant medication (e.g., trough of DTG or RIF, mid-dose concentration of EFV).
- 10.2.3.3 Human genetic variants/polymorphisms that are known to affect PK of EFV, DTG, RIF, or LNG (e.g., CYP2B6, SLCO1B1).
- 10.2.3.4 Acceptability and practicality of LNG based on participant self-report via study-specific questionnaires.

### 10.3 Randomization and Stratification

Enrollment to the study is deterministic (not-randomized) for participants who are currently taking either DTG based ART regimens, or RIF-containing anti-TB regimens; these women are directly assigned to Groups C and D, respectively. Participants on EFV-containing ART regimens will be randomized between Groups A (1.5 mg LNG) and B (3.0 mg LNG) in a 1:2 ratio using permuted block randomization that is dynamically balanced within each **institution**. To guard against potential confounding due to body weight or BMI of the participant, enrollment will be **limited** by BMI in the following manner. Women with BMI  $\geq 30$  kg/m^2 will be limited to no more than five within Groups B-D and no more than three within Group A. Therefore, the overall representation of obese women in the study sample will be limited to no more than 15%. The results of either randomization or enrollment to treatment group will be unblinded to participants, and clinical research site staff.

### 10.4 Sample Size and Accrual [53, 78-80]

Given that a therapeutic target for minimum exposure required or average exposure expected for single dose use of LNG as emergency contraception (EC) is unknown, this study is estimating whether adjusted dosing of LNG under a known DDI achieves similar exposure to LNG single dose as measured by the geometric mean ratio (GMR) of the AUC of LNG concentrations over the 8 hours post dose. The study design was developed under the constraints of requiring a parallel groups design (rather than a crossover design using healthy controls), practicalities of number of available participants to enroll and complete the study in a reasonable timeframe, and how the features of this highly variable drug (LNG) result in both power to test for bioequivalence as defined by a specified interval about equivalence, and precision of GMR estimates by the width of the 90% confidence interval.

The effective sample sizes of 30 women in Groups B-D and 15 women in Group A were chosen to provide adequate statistical precision about the estimated GMR, which compares arms in order to address the primary study objectives [54]. See below for the total sample size enrollment, which includes how these effective samples sizes are inflated slightly to accommodate missing primary outcome data.

Table 10.4-1: Sample size per arm (prior to inflation for replacements)

Assumptions: Sample size required to give 80% probability (power) to conclude bioequivalence defined as the 90% CI for the GMR being entirely within the No-effect Bounds (NEB). Various NEBs are provided for BE given that bounds of (80%, 125%) may be considered too conservative for highly variable drugs with a wide therapeutic ranges in PK exposure. [Note: Calculations use 5% significance level with two, one-sided tests (TOSTs) testing procedure.]

Sample Sizes per Arm in Table	Coefficient of Variation Estimates*								
	0.45			0.70			0.90		
Alternative Hypothesis (True GMR):	100%	95%	90%	100%	95%	90%	100%	95%	90%
NEB : (67%,150%)	20	22	27	43	45	57	63	67	84
NEB : (70%,143%)	26	28	37	55	59	79	81	87	117
NEB : (75%,133%)	40	45	72	85	97	154	126	144	228

\*Note: CV for AUC(0-24hr) ranged from 0.45 to 0.90 in the individual arms of PK study of LNG-EC and St. John's Wort (Time period 1 when LNG-EC given alone, ref ct.gov NCT00131885). Package insert for LNG CV(AUC24hr)=0.7. Data not available for CV of AUC or LNG-EC under shorter time frames.

Summary of Table 10.4-1. Because primary outcome of current study is AUC(0-8hr), it is assumed that the CV for this study may be on the lower range of published AUCs(LNG) over 24 hours. Furthermore, the sample sizes for CV  $\geq$  0.7 result in study sizes beyond feasibility for execution. NEBs of (80%, 125%) are not given in the table as the required sample would be too large, even under assumed CV=0.45.

Table 10.4-2: Statistical Power assuming n=30 per arm (prior to inflation for replacements)

Assumptions: same as Table 10.4-1 above [NEB = No-effect bounds]

Statistical Power Estimates in Table	Coefficient of Variation								
	0.45			0.70			0.90		
Alternative Hypothesis (True GMR):	100%	95%	90%	100%	95%	90%	100%	95%	90%
NEB : (67%,150%)	95%	93%	85%	58%	56%	50%	29%	28%	25%
NEB : (70%,143%)	88%	84%	72%	40%	38%	33%	12%	12%	10%
NEB : (75%,133%)	63%	58%	45%	9%	9%	7%	0%	0%	0%

Summary of Table 10.4-2 Assuming CV(AUC0-8hr) = 0.45, and other design assumptions above, BE bounds of either (67%, 150%) or (70%, 143%) provide high statistical power, even under modest departures from equivalence alternative (e.g., true GMR of between 90% and 100%). The study design is not well powered for NEBs narrower than (70%, 143%), or for departures from equivalence much larger than 10%

(i.e., true GMRs of less than 90%). Please see references [53, 78-80] that show precedence for using NEBs of (70%, 143%) in similar situations.

Table 10.4-3: Some CI estimates under various alternatives (sample size 30 per arm before inflation for replacements and same assumptions above)—simulation results.

Because the study analysis plan is focused on estimation of the GMR of AUC(LNG) and 90% CI about the estimated (observed) GMR, the following table is provided to augment the sample size/power tables above.

Alternative Hypothesis (True GMR)	CV=0.45				CV = 0.75			
	Q1 Observed GMR	Q3 Observed GMR	Median Observed GMR	Typical 90% CI (median LCB and UCB)	Q1 Observed GMR	Q3 Observed GMR	Median Observed GMR	Typical 90% CI (median LCB and UCB)
100%	93%	108%	100%	(83%, 120%)	90%	115%	100%	(75%, 133%)
95%	87%	103%	95%	(79%, 115%)	83%	108%	95%	(72%, 127%)
90%	84%	96%	89%	(74%, 107%)	81%	102%	90%	(68%, 120%)
85%	79%	93%	85%	(71%, 102%)	74%	95%	84%	(63%, 112%)

Alternative Hypothesis (True GMR)	CV=0.90			
	Q1 Observed GMR	Q3 Observed GMR	Median Observed GMR	Typical 90% CI (median LCB and UCB)
100%	88%	116%	102%	(73%, 141%)
95%	83%	110%	96%	(69%, 134%)
90%	76%	103%	89%	(64%, 124%)
85%	74%	97%	86%	(61%, 119%)

Summary of Table 10.4-3. Under modest departures from equivalence, the 90% CI about estimated GMRs observed to be 85% or closer to equivalence (100%) are expected to be bounded above the BE LCB of 70%.

The effective sample size for randomized Group A (15) is based on the secondary objective for a superiority hypothesis (rather than equivalence testing as in the primary study objectives), comparing the randomized Groups A and B (n=30). Here, the ratio is B/A so that the anticipated raw scale ratios are >100 and the significance level has been adjusted to 0.05 so that a 2-sided 95% CI is calculated and compared to see if the confidence interval excludes 100. There is at least 80% power to conclude a difference between the randomized groups for LNG AUC when the true difference between groups is that the increased dose has at least 47% larger AUC of LNG than the standard-dose (or estimated ratio 147.5). A 95% CI for this estimated ratio would be (112, 194).

A participant is considered to be evaluable for the primary objective if the participant completes the 8 hour PK sampling after LNG EC administration. The participant replacement criteria are described in [section 9.0](#). Participants who are not evaluable for the primary outcome for any reason during the period of study accrual will be replaced.

Considering the sample size calculations above, and to protect against 10% loss of the primary outcomes after study accrual is closed, (e.g., problems related to laboratory analysis), the adjusted sample size for this four-group study is 116 female participants—33 each in Groups B-D, and 17 in Group A. (In another ACTG contraception study, A5093, the loss of the primary outcomes of week 12 was 9.8% [6 of 61 participants] due to either sample specimen loss or assay results not available.)

Complete accrual to all study groups is anticipated to take between 1 year to 18 months. However, it is not assumed for this accrual to be uniform over this time period. Due to differences in regulatory approvals in different locations, it is anticipated that accrual during the first 6 months of the study may be exclusively from US sites. But it is anticipated that accrual will be rapid following the approval of the study at non-US CRSs. As an example, in a recent ACTG PK study investigating DDIs between ART and another contraceptive (A5316: NCT01903031), accrual within the first 6 months following first enrollment was only within the US and accounted for only 20% of total study accrual. However, in the following 6 month period when sites from an additional 6 countries were available, over 55% of the total study sample was accrued (and thus 77% of total study accrual occurred within 1 year). Therefore, it is anticipated that only 20% of the total sample size (or 23) women might be enrolled during the first 6 months following first participant enrollment, and that the remaining accrual will occur in the subsequent 6-12 months (which assumes enrollment of 8-16 women per month over this time period). Please see below for contingencies regarding a possible additional interim review if the total accrual at 12 months following first enrollment is <50% of the total sample size (i.e., fewer than 58 women).

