#### 2.1.1 Levonorgestrel (LNG)

Levonorgestrel is a progestational agent that inhibits ovulation by interrupting follicular development, and inhibits fertilization by altering the tubal transport of sperm and/or ova. In addition, it may inhibit implantation by altering the endometrium, but it is not effective once the process of implantation has begun [21]. LNG is commonly used in combination oral contraceptive pills, as EC, in progestin-releasing subdermal implants, and intrauterine devices. As EC, LNG should be taken within 72 hours after unprotected intercourse to prevent pregnancy. The absolute effectiveness of EC is difficult to determine because the rate varies with the timing of dosage with respect to unprotected intercourse, ovulation, and with the type of EC used. Estimates of LNG efficacy range from 59-94% [22]. In a multicenter randomized comparison of LNG versus ulipristal in nearly 1700 women presenting to family planning clinics for EC, there were 37 pregnancies with no statistical difference observed between the groups. To increase the power of the study, a meta-analysis was performed, and data from a total of 2221 women randomized to either ulipristal or LNG were compiled. This analysis confirmed that the pregnancy rate in both groups was lower than predicted, and that the pregnancy rate for LNG was 2.6% [23].

LNG for EC is typically given as a single 1.5 mg dose within 72 hours after intercourse. LNG reaches maximum concentration approximately 1.7 (range 1-4)

hours after administration and is 100% bioavailable after oral administration [21, 24, 25]. In 30 healthy, female volunteers, the mean (SD) LNG  $C_{max}$  was 19.1 (9.7) ng/mL, area under the curve  $(AUC)_{inf}$  was 307.5 (218.5) ng\*hr/mL, and half-life was 27.5 hours [21]. A clinical evaluation of another formulation of LNG (0.75 mg tablets, two tablets once) in five healthy volunteers found a geometric mean 44-hour (39-48-hours) half-life [26].

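### Do the summary sentences under protocol Tables 10.4-2 and 10.4-3 overstate the design's power and precision enough to need a change?

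*Protocol*

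**What the plan says.** Protocol 10.4 plans the two primary comparisons (Group B with C, Group D with C) at 30 effective women per arm, and sections 10.4 and 10.6.1 judge similarity by whether the 90% confidence interval for the GMR lies inside the no-effect bounds. Section 10.6.1 fixes those bounds at (70%, 143%).

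Three tables support the design. Table 10.4-1 lists the "Sample size required to give 80% probability (power) to conclude bioequivalence", Table 10.4-2 gives power at 30 per arm, and Table 10.4-3 gives simulated typical intervals at CV 0.45, 0.75 and 0.90.

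The working CV is openly an assumption: "it is assumed that the CV for this study may be on the lower range of published AUCs(LNG) over 24 hours". The note to Table 10.4-1 records that the "CV for AUC(0-24hr) ranged from 0.45 to 0.90 in the individual arms of PK study of LNG-EC", gives 0.7 from the package insert, and adds: "Data not available for CV of AUC or LNG-EC under shorter time frames".

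The two sentences at issue are these:

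- The summary of Table 10.4-2 first assumes CV 0.45. It then says that either (67%, 150%) or (70%, 143%) will "provide high statistical power, even under modest departures from equivalence alternative (e.g., true GMR of between 90% and 100" per cent). It goes on to concede that the design is not well powered for narrower bounds "or for departures from equivalence much larger than 10" per cent.
- The summary of Table 10.4-3, limited to modest departures from equivalence, says that intervals for "GMRs observed to be 85% or closer to equivalence (100%) are expected to be bounded above the BE LCB of 70" per cent. It names no CV.

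SAP 2.3 carries over one power figure, 88%, with its conditions (30 per group, CV 0.45, true GMR 100%, bounds 70% to 143%), and refers to the protocol for the rest.

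**The concern.** The 85% statement reads as a general rule, but it summarises a table with three CV columns and two of them contradict it. Five of the twelve printed typical lower bounds are below 70%: 68% and 63% at CV 0.75, and 69%, 64% and 61% at CV 0.90. Three of the five (68%, 69%, 64%) are at true GMRs of 90% or 95%, within what the protocol itself treats as modest departures.

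The power statement has a similar gap. For the chosen bounds the table prints 72% at true GMR 90%. That is below the 80% used to solve Table 10.4-1, which lists 37 per arm for that cell against 30 planned. The caveat that follows begins only below 90%, so it does not cover this cell.

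Because the plan puts weight on estimating the GMR and its interval, the 85% sentence is in effect the stated precision for both primary objectives. If the observed CV turned out well above 0.45, a GMR of 85% to 90% with a lower bound under 70% might surprise a reader who had relied on that sentence alone.

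**Working it through.** **Inputs.** n = 30 per arm (protocol 10.4); log-scale SD = √ln(CV² + 1), which is 0.429 at CV 0.45 (SAP 2.3); pooled variance (SAP 4.2.1); two one-sided 5% tests, equivalent to a 90% interval; bounds 0.70 and 1.43.

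**Step 1: reproduce the power table.** SE = 0.4294 × √(2/30) = 0.1109. With 58 degrees of freedom t = 1.672, so the half-width on the log scale is 1.672 × 0.1109 = 0.1853. At true GMR 0.90, holding the variance at its expected value:

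- lower bound cleared: Φ[(ln(0.90/0.70) − 0.1853)/0.1109] = Φ(0.595) = 0.724
- upper bound missed: 1 − Φ[(ln(1.43/0.90) − 0.1853)/0.1109] = 1 − Φ(2.50) = 0.006
- power ≈ 0.724 − 0.006 = 0.718

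Integrating over the sampling distribution of the pooled variance gives 87.6%, 83.7% and 71.8% at true GMR 100%, 95% and 90%, against 88%, 84% and 72% printed. All 27 cells of Table 10.4-2 agree within 2 points. For these bounds at CV 0.45, Table 10.4-1's 26, 28 and 37 per arm also reproduce. Power passes through 80% at a true GMR of about 93%. With all 33 enrolled women per arm evaluable, power at GMR 90% is 75.7%.

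**Step 2: the 85% rule.** Lower bound = observed GMR ÷ exp(t × SD × √(2/n)). The smallest observed GMR that clears 70% is 0.70 times the same factor.

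| CV | SD (log) | Factor | Lower bound at observed 85% | Smallest observed GMR clearing 70% | Typical lower bound printed at true GMR 85% |
|---|---|---|---|---|---|
| 0.45 | 0.4294 | 1.2036 | 70.6% | 84.3% | 71% |
| 0.75 | 0.6680 | 1.3342 | 63.7% | 93.4% | 63% |
| 0.90 | 0.7703 | 1.3944 | 61.0% | 97.6% | 61% |

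The limiting CV solves ln(0.85/0.70) = 1.672 × SD × √(2/30). So SD = 0.1942/0.4316 = 0.450, and CV = √(exp(0.450²) − 1) ≈ 0.47. At 33 per arm it is 0.50.

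**Step 3: what the two sentences feed into.** Protocol 10.6.1 and the statistical analysis table in SAP 3.1 compare the observed 90% interval with (0.70, 1.43). That interval uses the variance seen in the trial, not the planning CV. SAP 3.1 also reports the CV of AUC0-8h by group, so a reader can see which column of Table 10.4-3 applies. Neither sentence enters any calculation.

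**The case for a change.** The strongest case for acting is that CV 0.45 is the bottom of the cited range, the package insert gives 0.7, and no value exists for an 8-hour window. Even at 0.45 the rule holds by only 0.6 of a point. A rule that is true only near the most favourable CV ought to say so, and a few words would be enough. It is also fair that 72% falls short of the protocol's own 80% criterion.

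What stands is a missing qualifier in one sentence and a loose adjective in another. Three things keep it at that:

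- **Context supplies most of the condition.** The preceding summary opens by assuming CV 0.45, the title of Table 10.4-3 carries the earlier assumptions forward, and section 10.5.1 refers to a single CV estimate supporting the study size. Two of the five contrary rows (63% and 61%) are at true GMR 85%, outside the modest departures to which the sentence is limited.
- **The power sentence hides nothing.** The term is not defined, the 72% is printed in the table just above it, and 80% is the solving criterion of Table 10.4-1. The protocol says 30 per arm was chosen for adequate precision of the GMR.
- **A stronger claim depends on how the sentence is read.** With true GMR 90% and 30 per arm, among simulated trials observing 85% to 100%, the lower bound clears 70% in 41% at CV 0.75 and 17% at CV 0.90. If closeness to 100% is read symmetrically on the log scale (85% to 118%), the shares are 63% and 49%. So it cannot be said without qualification that most such trials would miss.

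Amending SAP 2.3 would edit a document that contains neither sentence and is already correct. Amending the protocol would need ethics approval at every site (section 4.3.1), after accrual has finished (SAP 1.2).

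**Conclusion.** The observation is accurate, but it is editorial. At 30 per arm the 85% rule holds up to a CV of about 0.47 (0.50 at 33 per arm), so it is right at the design CV of 0.45 and wrong for the table's other two columns. Power for the chosen bounds at CV 0.45 runs from 88% down to 72% as the true GMR goes from 100% to 90%, as the table prints. These figures assume log-normal AUC0-8h with equal variances, as the plan does.

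No stated power, sample size or interval is wrong, and adding the qualifier would only repeat figures already in the tables. The primary conclusions come from the observed interval, which will widen by itself if the true CV is larger. Anyone describing the design's precision in the analysis report can read the right column of Table 10.4-3. No change to the plan follows.
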